6.6. Appendix 6 Medical History

Not applicable

6.7. Appendix 7 Intervention Compliance

Compliance will be summarized descriptively based on the Randomized Analysis Set.

Additional listings of participants will be provided for the following categories:

- Participants who were randomized but did not receive study intervention
- Participants who were unblinded prior to Week 24 or Week 48

6.8. Appendix 8 Medications of Special Interest

Not applicable

6.9. Appendix 9 Laboratory Toxicity Grading

The grading scale used for lab assessments is based on 'Common Terminology Criteria for Adverse Events (CTCAE) v5.0'. Toxicity grades are based on the laboratory result and do not take into account the clinical component, if applicable.

Pre-baseline measurements will use the same grading ranges as applied to baseline measurements. In case a test has two sets of ranges — one for baseline normal and one for baseline abnormal, the one for baseline normal will be applied for all measurements taken pre-baseline and on baseline.

Table 15: Toxicity Grading Scale

Hematology Tests			Criter	ria .	
Test	Direction	1	2	3	4
Hemoglobin (g/dL)	Increase	>0 - 2 g/dL above ULN	>2 - 4 g/dL above ULN	>4 g ULN	1 7 - 21
Hemoglobin (g/dL)	Decrease	<lln -="" 10.0<="" td=""><10.0 - 8.0	<8.0	31 - 3	</lln>	<10.0 - 8.0	<8.0	3 1 - 3
Lymphocytes (/mm3)	Increase		>4000 - 20,000	>20,000	3 3
Lymphocytes (/mm3)	Decrease	<lln -="" 800<="" td=""><800 - 500	<500 - 200	<200	</lln>	<800 - 500	<500 - 200	<200
Neutrophils (/mm3)	Decrease	<lln -="" 1500<="" td=""><1500 - 1000	<1000 - 500	< 500	</lln>	<1500 - 1000	<1000 - 500	< 500
Platelets (/mm3)	Decrease	<lln -="" 75,000<="" td=""><75,000 - 50,000	<50,000 - 25,000	<25,000	</lln>	<75,000 - 50,000	<50,000 - 25,000	<25,000
Total WBC count (/mm3)	Increase	(L)	=	>100,000	9 - 0
Total WBC count (/mm3)	Decrease	<lln -="" 3000<="" td=""><3000 - 2000	<2000 - 1000	<1000	</lln>	<3000 - 2000	<2000 - 1000	<1000
Chemistry Tests		Criteria		V.	
Test	Direction	1	2	3	4
Albumin (g/L)	Decrease	≥30 - <lln< td="">≥20 - <30	<20		</lln<>	≥20 - <30	<20	
Corrected Calcium (mmol/L)	Increase	>ULN - ≤2.9	>2.9 - <3.1	>3.1 - ≤3.4	>3.4
Corrected Calcium (mmol/L)	Decrease	≥2.0 - <lln< td=""><2.0 - ≥1.75	<1.75 - ≥1.5	<1.5	</lln<>	<2.0 - ≥1.75	<1.75 - ≥1.5	<1.5
Creatinine	Increase	>ULN - ≤1.5 x ULN	>1.5 - 3.0 x baseline; >1.5 - 3.0 x ULN	>3.0 x baseline; >3.0 - 6.0 x ULN	>6.0 x ULN
Glucose (mmol/L)	Decrease	<lln -="" 3.0<="" td=""><3.0 - 2.2	<2.2 - 1.7	<1.7	</lln>	<3.0 - 2.2	<2.2 - 1.7	<1.7
Potassium (mmol/L)	Increase	>ULN - ≤5.5	>5.5 - 6.0	>6.0 - 7.0	>7.0
Potassium (mmol/L)	Decrease	8=8	<lln -="" 3.0<="" td=""><3.0 - 2.5	<2.5	</lln>	<3.0 - 2.5	<2.5
Sodium (mmol/L)	Increase	>ULN - 150	>150 - 155	>155 - 160	>160
Sodium (mmol/L)	Decrease	<lln -="" 130<="" td="">=	-<130-120	<120	</lln>	=	-<130-120	<120

Table 16: Liver Function Tests

Liver Function Tests	ULN Thresholds	
ALT/AST	>1x to <3x ULN	
	$\geq 3x$ to $\leq 5x$ ULN	
	\geq 5x to <8x ULN	
St.	≥8 x ULN	100
Alkaline Phosphatase	>1 to <2 x ULN	
	≥ 2 x to ≤ 4 x ULN	
	≥4 x ULN	
Total Bilirubin	>1x to <2x ULN	
	≥2x ULN	

6.10. Appendix 10 Mayo Score

Table 17 shows the Mayo scoring system^{1),10)}.

6.11. Appendix 11 Geboes Score

Table 18 shows the Geboes²⁾ grading criteria.

[figure not shown]
Table 18: Geboes score

Grade 0	Structural (architectural change)
Subgrades	. 57
0.0	No abnormality
0.1	Mild abnormality
0.2	Mild or moderate diffuse or multifocal abnormalities
0.3	Severe diffuse or multifocal abnormalities
Grade 1	Chronic inflammatory infiltrate
Subgrades	
1.0	No increase
1.1	Mild but unequivocal increase
1.2	Moderate increase
1.3	Marked increase
Grade 2	Lamina propria neutrophils and eosinophils
2A Eosinophils	
2A.0	No increase
2A.1	Mild but unequivocal increase
2A.2	Moderate increase
2A.3	Marked increase
2B Neutrophils	
2B.0	No increase
2B.1	Mild but unequivocal increase
2B.2	Moderate increase
2B.3	Marked increase
Grade 3	Neutrophils in epithelium
3.0	None
3.1	<5% crypts involved
3.2	<50% crypts involved
3.3	>50% crypts involved
Grade 4	Crypt distruction
4.0	None
4.1	Probable – local excess of neutrophils in part of crypt
4.2	Probable – marked attenuation
4.3	Unequivocal crypt destruction
Grade 5	Erosion or ulceration
5.0	No erosion, ulceration, or granulation tissue
5.1	Recovering epithelium + adjacent inflammation
5.2	Probable erosion – focally stripped
5.3	Unequivocal erosion
5.4	Ulcer or granulation tissue

6.12. Appendix 12 Nancy Histological Index

[figure not shown]
Figure 3 shows the grading for the Nancy histological index⁵.

Figure 3: Nancy histological index

6.13. Appendix 13 Robarts Histopathology Index

Table 19 shows the definition of the Robarts histopathology index⁷.

[figure not shown]
6.14. Appendix 14 Detailed Prohibited Changes in UC Medications Rules

[figure not shown]
Participants had a prohibited change in UC medication described below are considered to have experienced ICE 2 as defined in Table 6:

[figure not shown]
- Initiation of restricted medications (rectal 5-ASA compounds, parenteral or rectal corticosteroids, including budesonide and beclomethasone dipropionate)
- Initiation of the following prohibited concomitant therapies
 - Immunomodulatory agents other than 6-MP, AZA, or MTX (eg, 6-thioguanine, cyclosporine, mycophenolate mofetil, tacrolimus, sirolimus, ozanimod, tofacitinib, and other JAK inhibitors).
 - Immunomodulatory biologic agents (eg, TNFα antagonists, ustekinumab, vedolizumab, abatacept, anakinra).
 - Experimental IBD medications (eg, upadacitinib, etrolizumab, brazikumab, mirikizumab, risankizumab) or other investigational medications/therapies.
 - Thalidomide or related agents
- Initiation of oral corticosteroids (including budesonide and beclomethasone dipropionate) due to worsening of disease.
- Increase in the dose of oral corticosteroids (excluding budesonide and beclomethasone dipropionate) > 5 mg/day (prednisone equivalent) above the baseline dose due to worsening of disease:
 - Any number of days with increase from Week 0 through Week 12
 - 3 days or more with increase from Week 12 through Week 24
 - 7 days or more with increase from Week 24 through Week 48
- Increase in the dose of oral budesonide > 3 mg/day above the baseline dose due to worsening of disease:
 - Any number of days with increase from Week 0 through Week 12
 - 3 days or more with increase from Week 12 through Week 24
 - 7 days or more with increase from Week 24 through Week 48
- Increase in the dose of oral beclomethasone dipropionate > 5 mg/day above the baseline dose due to worsening of disease:
 - Any number of days with increase from Week 0 through Week 12
 - 3 days or more with increase from Week 12 through Week 24
 - 7 days or more with increase from Week 24 through Week 48
- Any switch among oral budesonide, oral beclomethasone dipropionate or other oral corticosteroids (excluding prednisone equivalent changes) due to worsening of disease.
- Initiation of oral 5-ASA compounds due to worsening of disease.
- Increase above baseline in the dosage of oral 5-ASA compounds due to worsening of disease.

- Change from one oral 5-ASA compound to another 5-ASA compound due to worsening of disease.
- Initiation of 6-MP/AZA/MTX due to worsening of disease.
- Increase above baseline in the dosage of 6-MP/AZA/MTX due to worsening of disease.
- Any switch between 6-MP/AZA and MTX due to worsening of disease.

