6.8.1. UC-related Concomitant Therapies

Week 0 through Week 48

Participants who are receiving oral 5-ASA compounds, oral corticosteroids, or conventional immunomodulators (AZA, 6-MP, or MTX) for the treatment of UC at baseline should maintain a stable dose through Week 48; with the exception of oral corticosteroids which require mandatory tapering at Week 12 as described in Section 6.8.1.1.

From Week 0 through Week 48, enrolled participants should not initiate any of the following concomitant UC-specific medical therapies at any time:

- Oral or rectal 5-ASA compounds.
- Oral, parenteral, or rectal corticosteroids, including budesonide and beclomethasone dipropionate.
- 6-MP, AZA, or MTX.
- Antibiotics as a primary treatment for UC.
- Total parenteral nutrition as a treatment for UC.

If the above medical therapies are initiated or medication doses are changed based on medical necessity as assessed by the investigator, participants should continue to attend all study visits and have all assessments. This does not represent a deviation from the study protocol and the participants may remain on their assigned therapy (guselkumab or placebo).

Week 48 through Week 248

Concomitant therapies for UC, including 5-ASA compounds, corticosteroids, antibiotics, immunomodulators (ie, AZA, 6-MP, or MTX), and/or total parenteral nutrition, may be administered and changed at the discretion of the investigator.

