2. A prohibited change in medications for UC (as	treated as an unfavorable outcome
defined in Appendix 14)	
3. Discontinuation from study intervention due to lack	
of efficacy or an adverse event (AE) of UC worsening	
4. Meeting rescue criteria (as determined by the IWRS)	
(Note: Since rescue criteria are assessed at Week 16	
for all participants, this ICE is not applicable for the	
primary endpoint or any of the key secondary Week 12	
endpoints)	
5. Discontinuation of study intervention due to	Treatment policy strategy: Observed values will be
COVID-19 related reasons (excluding COVID-19	used if available
infection) or regional crisis	
6. Discontinuation of study intervention due to reasons	Composite strategy: Occurrence of these ICEs will be
other than ICEs 3 or 5 as described above	treated as an unfavorable outcome

The composite strategy assesses the treatment effect not only based on the variable measurements, but also on ICEs. This estimand acknowledges that having an ICE in categories 1-4 and 6 is an unfavorable outcome. For participants experiencing an ICE in category 5, the treatment policy strategy considers the occurrence of ICE category 5 as irrelevant in defining the treatment effect.

v) Population-level summary: Difference in proportions of participants who achieved the binary response at Week 12 as defined in the variable attribute above between the combined guselkumab group and the placebo group.

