6.5. Appendix 5 Prior and Concomitant Medications

Concomitant therapies received at baseline can only be discontinued or reduced in dose during the study as described below.

Week 0 Through Week 48

For those participants who are starting the study on approved concomitant medications, the following instructions apply:

- Participants who are receiving oral 5-ASA compounds at baseline (ie, Week 0) should maintain a stable dose through Week 48.
- Corticosteroids must be maintained at baseline doses through Week 12. Participants must begin tapering corticosteroids at Week 12 unless medically not feasible.
- Immunomodulators must be maintained at baseline doses through Week 48.

Enrolled participants should not initiate any of the following concomitant UC-specific medical therapies through Week 48:

- Oral or rectal 5-ASA compounds.
- Oral, parenteral, or rectal corticosteroids, including budesonide and beclomethasone dipropionate.
- 6-MP, AZA, or MTX.
- Antibiotics as a primary treatment for UC.
- Total parenteral nutrition as a treatment for UC.

Week 48 through Week 96

Concomitant therapies for UC, including 5-ASA compounds, corticosteroids, antibiotics, immunomodulators (ie, AZA, 6-MP, or MTX), and/or total parenteral nutrition, may be administered and changed at the discretion of the investigator.

Oral Corticosteroids Tapering

Participants who are receiving oral corticosteroids for the treatment of UC at baseline (Week 0) should maintain a stable dose through Week 12. The oral corticosteroid dose should not be increased above the baseline dose unless due to medical necessity.

At Week 12, all participants who were taking corticosteroids at Week 0 must begin tapering corticosteroids. This tapering is mandatory (unless medically not feasible) and should follow the recommended schedule shown in Section 6.8.1.1 of the study protocol. If participants experience worsening disease activity while tapering corticosteroids, further dose decreases may be suspended, and/or their oral corticosteroid dose may be temporarily increased up to their baseline corticosteroid dose per the discretion of the investigator. For participants whose corticosteroid taper is interrupted, investigators are encouraged to resume tapering within 4 weeks. Tapering may exceed this schedule only if warranted by medical necessity (eg, participant experiencing

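### SAP Appendix 14 leaves two of the five UC therapies that participants should not start (UC antibiotics and parenteral nutrition) out of ICE 2, so a user can be scored as a responder

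*SAP*

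**What the plan says.** Protocol 6.8.1 sets the rule on starting UC therapy: "From Week 0 through Week 48, enrolled participants should not initiate any of the following concomitant UC-specific medical therapies at any time". SAP Appendix 5 repeats it: "Enrolled participants should not initiate any of the following concomitant UC-specific medical therapies through Week 48". Both give the same five classes: 5-ASA, corticosteroids, 6-MP/AZA/MTX, "Antibiotics as a primary treatment for UC", and "Total parenteral nutrition as a treatment for UC".

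Protocol 6.8.1 also allows a start for medical necessity. In that case: "This does not represent a deviation from the study protocol and the participants may remain on their assigned therapy (guselkumab or placebo".

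On the analysis side, SAP Table 6 lists the event as "2. A prohibited change in medications for UC (as", and the row goes on to cite Appendix 14. ICE 2 takes the composite strategy, so it counts as an unfavourable outcome. Appendix 14 makes its own list the operative definition: "Participants had a prohibited change in UC medication described below are considered to have experienced ICE 2 as defined in Table 6". The first item is "Initiation of restricted medications (rectal 5-ASA compounds, parenteral or rectal corticosteroids, including budesonide and beclomethasone dipropionate". The remaining items are the prohibited agents of Protocol 6.8.2 and changes in oral corticosteroids, oral 5-ASA and 6-MP/AZA/MTX.

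**The concern.** Two lists that should correspond do not. The conduct rule names five classes, and the analysis rule picks up three of them. The two left out are treatments given for the disease under study, and a start of either could help a participant meet an endpoint on observed data. Because the plan counts starts of the other three classes as failure, at least when due to worsening, credit for these two would go to the assigned arm under a rule that treats similar therapies differently and does not say why.

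The same ICE 2 list is used beyond the primary endpoint. It applies to all secondary endpoints (SAP 5.4.1.2) and to the binary exploratory endpoints (SAP 5.5.4). For continuous endpoints it also decides when baseline values replace observed ones.

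**Working it through.** **Step 1. The two lists side by side.**

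| Class not to be started (Protocol 6.8.1, SAP Appendix 5) | Is a start counted in SAP Appendix 14? |
|---|---|
| 5-ASA, oral or rectal | Rectal: yes, without condition. Oral: yes, if due to worsening |
| Corticosteroids, oral, parenteral or rectal | Parenteral or rectal: yes, without condition. Oral: yes, if due to worsening |
| 6-MP, AZA, MTX | Yes, if due to worsening |
| Antibiotics as primary UC treatment | Not mentioned |
| TPN for UC | Not mentioned |

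Five classes are listed, three are counted and two are absent.

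**Step 2. Does another ICE catch these users?** Take a participant who starts a UC antibiotic or TPN before Week 12 and remains on study intervention.

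- ICE 1 (ostomy or colectomy): not triggered by the start.
- ICE 2: not on the list.
- ICEs 3, 5 and 6 (discontinuations): not triggered, because Protocol 6.8.1 lets the participant stay on assigned therapy.
- ICE 4 (rescue criteria): depends on Mayo scores, not on medication, and does not apply to Week 12 endpoints.

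The participant is therefore analysed on observed subscores and is a responder if they meet the definition. Supplementary Estimands 2 and 5 change only the handling of discontinuations and keep ICE 2 as it is. The sensitivity analyses in SAP 5.3.3.3 vary assumptions about missing data, so they do not reach users with observed outcomes.

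**Step 3. Size per participant.** Planned numbers are 133 per group, so 266 against 133 at Week 12. These are crude differences, without stratum weights.

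- Week 12, guselkumab responder reclassified: 1/266 = 0.38 points, lowering the difference.
- Week 12, placebo responder reclassified: 1/133 = 0.75 points, raising the difference.
- Week 24, either arm of a pairwise comparison: 1/133 = 0.75 points.

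**Step 4. The plan's own figure, then an illustration.** Neither document gives a rate of antibiotic or TPN use. The nearest stated figure is primary power above 95% for 22% versus 8%. With the pooled-variance normal approximation to the two-sided chi-square test at 0.05:

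z = (0.14 − 1.96 × √[0.1733 × 0.8267 × (1/266 + 1/133)]) / √[0.22 × 0.78/266 + 0.08 × 0.92/133] = (0.14 − 0.0788)/0.0346 = 1.77

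This gives power of 96.2%, so the stated figure reproduces. The fix does not alter it. Purely as an assumption, suppose 0% to 10% of Week 12 remitters in an arm were reclassified:

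| Reclassified, guselkumab / placebo | Rates | Difference | Power |
|---|---|---|---|
| 0% / 0% | 22.0% vs 8.0% | 14.0 points | 96.2% |
| 5% / 5% | 20.9% vs 7.6% | 13.3 points | 95.0% |
| 10% / 10% | 19.8% vs 7.2% | 12.6 points | 93.6% |
| 10% / 0% | 19.8% vs 8.0% | 11.8 points | 89.2% |
| 0% / 10% | 22.0% vs 7.2% | 14.8 points | 98.0% |

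The effect can go either way. Ten percent of assumed remitters would be about 6 guselkumab participants (0.10 × 0.22 × 266 = 5.9) or 1 placebo participant (0.10 × 0.08 × 133 = 1.1).

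**The case against.** The best defence is that the omission is deliberate. ICE 2 concerns a prohibited change, Protocol Tables 8 and 11 do not itemise it, and neither antibiotics nor TPN is on the prohibited list in Protocol 6.8.2. Appendix 14 is also a graded rule set: it tolerates small oral steroid increases, tolerates short ones after Week 12, and counts many changes only when due to worsening. TPN is arguably nutrition rather than medication.

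Part of this stands. Nothing in the documents obliges Appendix 14 to mirror Protocol 6.8.1, so intent cannot be settled from the text. Three points weigh against it:

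- 5-ASA, corticosteroids and 6-MP/AZA/MTX are not in Protocol 6.8.2 either, yet Appendix 14 counts them.
- Inclusion criterion 10.1 (items g to k) gives rectal corticosteroids, rectal 5-ASA, parenteral corticosteroids, TPN and UC antibiotics the same two-week washout. The first item of Appendix 14 covers the first three and stops there.
- SAP Appendix 4 points to Appendix 5 for prohibited-medication deviations, and Appendix 5 names both therapies. SAP Appendix 2 reports no change to the planned analyses.

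A reader might also infer that these therapies are forbidden outright. They are not: the wording is that participants should not start them, with an allowance for medical necessity.

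It is also fair to say that many worsening participants will be caught elsewhere, through discontinuation or, at Week 24, the rescue criteria. To matter, a user must avoid every other ICE and still meet the endpoint.

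**Conclusion.** The gap is real and minor. As written, Appendix 14 lets a participant who starts a UC antibiotic or TPN, and stays on assigned therapy, count as a responder. Few participants are expected, although that is a judgement because no usage rates are given. The effect is 0.38 or 0.75 points per person at Week 12 and 0.75 points at Week 24.

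Two further inferences should be resisted. A reader might conclude that the gap favours guselkumab; the documents do not support any direction. If use were commoner on placebo, the extra placebo responders would shrink the difference, which is conservative for a superiority claim. A reader might also conclude that symptom-based endpoints, including clinical response, are most exposed. Nothing in the documents ranks the endpoints, and clinical response rests on the modified Mayo score, which includes endoscopy.

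The conclusion assumes that the bulleted list in Appendix 14 is complete. Two figures in that appendix are not shown in the public text. The list reads as whole without them, but this cannot be confirmed.

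**What to change.** Add two items to SAP Appendix 14: initiation of antibiotics where the recorded indication is primary treatment of UC, and initiation of TPN where the recorded indication is treatment of UC. Protocol 6.8 already requires the indication of every concomitant therapy to be recorded, so antibiotics for infection can be separated without new data. If the omission was intended, say so in Appendix 14 and give the reason.

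Timing matters, because this changes the variable in the primary estimand, and Protocol 9.4 requires the SAP to be final before the Week 24 database lock. The documents do not say whether that lock has passed. If it has, leave the primary definition as it is, report the number of users by arm, and add a clearly labelled sensitivity analysis that counts them as nonresponders.

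The cost is two lines of SAP text and a short derivation from concomitant-therapy records, or one extra table and one extra analysis after lock. The change affects the analysis rule only, not participant care.

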 - 2) History of an inadequate response to or intolerance of at least 1 of the following therapies: oral or IV corticosteroids or immunomodulators (6-MP or AZA) as defined in Appendix 2 (Section 10.2).
 OR
 - 3) History of corticosteroid dependence (ie, an inability to successfully taper corticosteroids without a return of the symptoms of UC) as defined in Appendix 2 (Section 10.2).
- 9. Criterion modified per Amendment 1
 - 9.1 Before the first dose of study intervention, the following conditions must be met:
 - a. If receiving conventional immunomodulators (ie, AZA, 6-MP, or MTX), must have been taking them for \ge 12 weeks, and on a stable dose for at least 4 weeks.
 - b. If AZA, 6-MP, or MTX has been recently discontinued, it must have been stopped for at least 4 weeks.
 - c. If receiving oral 5-ASA compounds, the dose must have been stable for at least 2 weeks.
 - d. If receiving oral corticosteroids other than budesonide or beclomethasone dipropionate, the dose must be ≤20 mg/day prednisone or its equivalent and must have been stable for at least 2 weeks.
 - e. If receiving oral budesonide or beclomethasone dipropionate, the dose must be ≤9 mg/day of budesonide, or ≤5 mg/day beclomethasone dipropionate and have been stable for at least 2 weeks.

- f. If oral 5-ASA compounds or oral corticosteroids have been recently discontinued, they must have been stopped for at least 2 weeks.
- 10. Criterion modified per Amendment 1
 - 10.1 The following medications/therapies must have been discontinued before the first dose of study intervention:
 - a. TNF α -antagonist therapy (eg, infliximab, adalimumab, or golimumab [or approved biosimilars for these therapies]) for at least 8 weeks.
 - b. Vedolizumab for at least 12 weeks.
 - Note for a and b: If there is proper documentation of an undetectable drug level measured by the site using a commercially available assay for any of the approved biologics above, there is no minimum washout prior to baseline.
 - c. Tofacitinib, filgotinib, upadacitinib and other JAK inhibitors for at least 2 weeks or 5 half-lives, whichever is longer.
 - d. Ozanimod or other S1PR modulators for at least 4 weeks or 5 half-lives, whichever is longer.
 - e. Cyclosporine, mycophenolate mofetil, tacrolimus, or sirolimus for at least 4 weeks.
 - f. 6-thioguanine must have been discontinued for at least 4 weeks.

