SAE serious adverse event SAP statistical analysis plan

SARS-CoV-2 severe acute respiratory coronavirus syndrome coronavirus 2

SC subcutaneous
SD standard deviation
SF stool frequency
SFU safety follow-up
SoA Schedule of Activities

SUSAR suspected unexpected serious adverse reactions

T Telemedicine Visit
TB tuberculosis
Tbili total bilirubin
TNF tumor necrosis factor
UC ulcerative colitis

CCI

ULN upper limit of normal WBC white blood cells

Definitions of Terms

COA An umbrella term encompassing different types of outcomes assessments.

Electronic source

system

Contains data traditionally maintained in a hospital or clinic record to document medical care or data recorded in a CRF as determined by the protocol. Data in this system may be

considered source documentation.

PRO Reports directly from the patient without interpretation by clinician or anybody else.

10.2. Appendix 2: Definition of Inadequate Response to or Intolerance of Corticosteroids or AZA/6-MP and Corticosteroid Dependence

CORTICOSTEROIDS

Participants have failed to respond to corticosteroids if they have had evidence of an initial inadequate response, recurrent disease, or a relapse despite receiving at least 0.75 mg/kg/day or \geq 40 mg/day of prednisone (or corticosteroid equivalent, given orally or intravenously) for 2 weeks; or \geq 9 mg/day of budesonide or \geq 5 mg/day of beclomethasone dipropionate given orally for at least 4 weeks.

Participants are intolerant of corticosteroids if:

• They have developed clinically significant adverse events (eg, osteonecrosis or osteoporosis, psychosis, uncontrolled diabetes) unresponsive to dose reduction that, in the judgment of the investigator, precluded the use of corticosteroids to treat ulcerative colitis (UC).

OR

• They have a medical condition that precludes the use of corticosteroids as a treatment for UC.

Participants are corticosteroid dependent if they have failed to successfully taper their corticosteroid (ie, had a flare of disease) within 12 weeks of starting therapy, or if a relapse occurs within 12 weeks after stopping corticosteroids or if they are unable to discontinue these agents without flare within 12 weeks after starting them.

6-MERCAPTOPURINE (6-MP) OR AZATHIOPRINE (AZA)

Participants have failed to respond to 6-MP or AZA if they have had evidence of an initial inadequate response, recurrent disease, or a relapse despite receiving:

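### Doubling oral beclomethasone for worsening UC can never be ICE 2, because the SAP trigger (more than 5 mg/day above baseline) is as large as the protocol's entry cap (5 mg/day)

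*SAP*

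**What the plan says.** SAP Table 6 (Section 5.3.2.1) handles ICE 2, a prohibited change in UC medication, by the composite strategy, and Appendix 14 (Section 6.14) defines it. The oral steroid lines in Appendix 14 are:

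- Other oral corticosteroids: "Increase in the dose of oral corticosteroids (excluding budesonide and beclomethasone dipropionate) > 5 mg/day (prednisone equivalent) above the baseline dose", when due to worsening of disease.
- Budesonide: "Increase in the dose of oral budesonide > 3 mg/day above the baseline dose due to worsening of disease".
- Beclomethasone: "Increase in the dose of oral beclomethasone dipropionate > 5 mg/day above the baseline dose due to worsening of disease".
- New starts: "Initiation of oral corticosteroids (including budesonide and beclomethasone dipropionate) due to worsening of disease".
- Any switch among these steroids because of worsening.

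Each of the three dose-increase lines carries the same duration rule. For the primary endpoint it is "Any number of days with increase from Week 0 through Week 12", with longer minimum durations after Week 12.

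Protocol Section 5.1, criterion 9.1, limits the steroid dose at entry. For prednisone-type steroids, "the dose must be ≤20 mg/day prednisone or its equivalent"; for the other two, "the dose must be ≤9 mg/day of budesonide, or ≤5 mg/day beclomethasone dipropionate".

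Protocol Section 6.8.1.1 asks that the oral steroid dose not go above baseline unless medically necessary. Section 6.8.1 adds that a medically necessary change is not a deviation and that the participant may stay on assigned treatment. ICE 2 is therefore the rule that decides how such an increase is scored. Neither document gives a reason for the beclomethasone threshold.

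**The concern.** The composite strategy is meant to stop a participant from counting as a responder after UC treatment has been stepped up for a flare. For beclomethasone the step needed to trigger it is the full entry maximum, so a same-drug doubling passes unscored from every permitted starting dose. For the other two steroids, doubling from the entry cap is scored.

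The rule is also uneven within beclomethasone. A non-user who starts it at 5 mg/day for worsening has ICE 2; a baseline user at 5 mg/day who adds another 5 mg/day for the same reason does not.

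ICE 2 enters the primary variable and every Week 12 and Week 24 secondary variable (SAP Sections 5.3.2.1 and 5.4.1.2). Supplementary Estimands 2 and 5 keep it under the composite strategy, so they would not reveal the gap. What is at stake is whether like events are scored alike in the confirmatory endpoints.

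**Working it through.** The plan states no figure on this point, so there is none to reproduce. The check is arithmetic on the dose limits, followed by a search for any other line that would catch the increase.

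**1. When does doubling trigger ICE 2?** Let b be the baseline dose, C the entry cap (Protocol 5.1, criterion 9.1) and T the trigger (SAP Appendix 14). Doubling adds b, and ICE 2 occurs only if b > T.

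| Oral steroid | C (mg/day) | T (mg/day) | T/C | Doubling from the cap | ICE 2? | Total dose above which the rule fires from the cap |
|---|---|---|---|---|---|---|
| Prednisone equivalent | 20 | >5 | 5/20 = 25% | +20 | yes | 25 |
| Budesonide | 9 | >3 | 3/9 = 33% | +9 | yes | 12 |
| Beclomethasone | 5 | >5 | 5/5 = 100% | +5 | no | 10 |

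The inequality is strict, so +5 does not trigger. Doubling also escapes for prednisone baselines up to 5 of the permitted 20 mg/day and budesonide baselines up to 3 of the permitted 9. For beclomethasone it escapes over the whole permitted range. At b = 2.5 even tripling (+5) escapes; at b = 3 tripling (+6) triggers.

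**2. Does another line catch it?** The general steroid line excludes beclomethasone. The initiation line needs a new start and the switch line needs a change of drug. No other Appendix 14 line covers an increase in the same drug.

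**3. Is the scale out of line with the documents' own figures?** Criterion 9.1e sets beclomethasone 5 mg/day beside budesonide 9 mg/day. Protocol Appendix 2 (Section 10.2) does so again when it defines steroid failure: at least 9 mg/day of budesonide, or at least 5 "mg/day of beclomethasone dipropionate given orally for at least 4 weeks". Yet the trigger is 3 for budesonide and 5 for beclomethasone. Against the Appendix 2 doses (40, 9 and 5 mg/day) the triggers are 5/40 = 12.5%, 3/9 = 33% and 5/5 = 100%.

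**4. How many participants?** The documents do not say how many use oral beclomethasone. Assume 1% to 3% of 399, which is 4 to 12 users over all three arms. Misclassification also needs an increase for worsening of 5 mg/day or less, all endpoint criteria met, and no other composite ICE. As an illustration, assume that 20% of users have such an increase and that they remit at the planned guselkumab rate of 22%, which is generous for participants who flared:

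- 4 × 0.20 × 0.22 = 0.2 participants
- 12 × 0.20 × 0.22 = 0.5 participants
- extreme case, all 12 escalate: 12 × 0.22 = 2.6 participants

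For clinical response at Week 12, with the planned guselkumab rate of 60%: 12 × 0.20 × 0.60 = 1.4 participants.

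**5. Size per participant.** 1/266 = 0.38 points in combined guselkumab and 1/133 = 0.75 points in placebo, against a planned Week 12 difference of 22 − 8 = 14 points.

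**The case against.** The strongest reply is that the entry caps are eligibility limits while the triggers are tolerances around each participant's own baseline, and nothing in the documents ties one to the other. In absolute terms the beclomethasone trigger equals the prednisone-equivalent one, and all three steroids have a tolerance band. This stands in part. With no dose equivalence given, the documents support calling the threshold unexplained and inconsistent in scale, but not calling any particular figure wrong. It does not remove the inconsistency, because the protocol pairs 5 mg of beclomethasone with 9 mg of budesonide in two places and the SAP triggers run the other way.

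A reader might infer that the beclomethasone line is dead, or that flares in beclomethasone users go unseen. The documents do not support that. The line fires above +5 mg/day. A flare is still caught by a switch of oral steroid, by parenteral or rectal steroids, by starting or raising 5-ASA or 6-MP/AZA/MTX, by a prohibited immunomodulator or biologic, by stopping study treatment (ICE 3 or 6) and, at Week 24, by meeting rescue criteria (ICE 4). The corticosteroid-free endpoints (SAP Section 5.5.1.3) also exclude anyone receiving corticosteroids at the assessed time.

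A reader might also infer a bias in favour of guselkumab. If placebo participants need more escalation, missed ICEs would raise the placebo rate and shrink the difference, which is conservative for superiority. Missed ICEs in the guselkumab arms would act the other way. The net direction cannot be determined from the documents.

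**Conclusion.** The point holds as a small inconsistency in an analysis rule. From every eligible baseline, a same-drug doubling of beclomethasone for worsening UC is not ICE 2, and such a participant could count as a responder if all endpoint criteria are met and no other composite ICE occurs. That conclusion needs only the two documents' own limits.

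The size rests on assumptions about the share of users and the frequency of escalation. On those, the expected number misclassified is probably below one to a few, at 0.38 or 0.75 points each. The 4 to 12 are assumed users, not misclassified responders. Nothing here suggests that the primary conclusion would change. The point says nothing about which beclomethasone dose is clinically right.

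**What to change.** For the analysis rule only, and before unblinding:

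- Reconcile the Appendix 14 beclomethasone trigger with the entry caps in criterion 9.1, so that it is on a scale consistent with the prednisone and budesonide triggers, or state the reason for the present threshold. The duration rules can stay. Counting any increase, as Appendix 14 does for 5-ASA and immunomodulators, would close the gap but make beclomethasone stricter than the other two steroids, which keep a tolerance; as the main rule it would need its own justification.
- Report by arm the number of beclomethasone increases for worsening that are at or below the trigger, with a sensitivity analysis of the primary and secondary endpoints that scores them as ICE 2.

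Protocol Section 10.6.4 says that recruitment has stopped, and the documents do not show whether the Week 24 lock has taken place. If it has, the main rule should stay as it is and the count and sensitivity analysis should be labelled post hoc.

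The cost is one line in Appendix 14 and one short table. A few participants may move to non-response. No clinical dose is proposed.
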